- Q3. hours missed due to other reasons in the last seven days
- Q4. hours actually worked in the last seven days
- Q5. degree hepatitis C affected productivity while working
- Q6. degree hepatitis C affected regular activities

The four scores will be derived as follows:

1. % absenteeism: $100 \times Q2 / (Q2 + Q4)$
2. % presenteeism: $100 \times Q5 / 10$

Confidential Information

No use or disclose outside AbbVie is permitted without prior written authorization from AbbVie

Version 3.0 (22 Apr 2015) – country v 1.0 dated 26.06.2015

Page 38 of 61

3. % TWP: $100 * \{Q2/(Q2+Q4) + [Q4/(Q2+Q4)] * Q5/10\}$
4. % TAI: $100 * Q6/10$

A score will be set to missing if one or more of the items Q1-Q6 that are needed for the calculation of the score are missing. No imputation will be performed for missing items.

The summary table will present the absolute and relative frequencies of employed and unemployed patients and descriptive statistics for the four scores. Further details of the analysis will be specified in the SAP.

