Annex 2. WPAI

Work Productivity and Activity Impairment Questionnaire Hepatitis C, V2.0 (WPAI: Hepatitis C)

The following questions ask about the effect of your hepatitis C on your ability to work and perform normal daily activities. *Please fill in the blanks or circle a number, as indicated.*

1) Are you currently in paid employment? NO YES
If NO, tick "NO" and skip to question 6.

The next questions refer to the **past seven days**, not including today.

2) During the past seven days, how many hours did you miss from work because of problems associated with your hepatitis C? *Include hours you missed on sick days, times you went in late, left early, etc., because of your hepatitis C. Do not include time you missed to participate in this study.*

HOURS

3) During the past seven days, how many hours did you miss from work because of any other reason, such as annual leave, holidays, time off to participate in this study?

HOURS

4) During the past seven days, how many hours did you actually work?

HOURS *(If "0", skip to question 6.)*

[figure not shown]
Confidential Information

No use or disclose outside AbbVie is permitted without prior written authorization from AbbVie
Version 3.0 (22 Apr 2015) – country v 1.0 dated 26.06.2015 Page 54 of 61

5. During the past seven days, how much did hepatitis C affect your productivity while you were working?

Think about days you were limited in the amount or kind of work you could do, days you accomplished less than you would like, or days you could not do your work as carefully as usual. If hepatitis C affected your work only a little, choose a low number. Choose a high number if hepatitis C affected your work a great deal.

[figure not shown]
Consider only how much hepatitis C affected productivity while you were working.

6. During the past seven days, how much did your hepatitis C affect your ability to perform your normal daily activities, excluding your job?

By normal activities, we mean the usual activities you perform, such as working around the house, shopping, childcare, exercising, studying, etc. Think about times you were limited in the amount or kind of activities you could perform and times you accomplished less than you would like. If hepatitis C affected your activities only a little, choose a low number. Choose a high number if hepatitis C affected your activities a great deal.

Consider only how much hepatitis C affected your ability to perform your normal daily activities, excluding your job.

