### 10.2 WPAI

Assessments of work productivity and activity impairment as assessed by the WPAI Hepatitis C will be evaluated according to the WPAI:SHP v2.0 scoring manual.

The following WPAI parameters will be analyzed:

- the WPAI Hep C v2.0 question answers;
- the WPAI:SHP scores.

The WPAI Hep C v2.0 consists of six questions:

- currently employed (Q1);
- hours missed due to hepatitis C in the last seven days (Q2);
- hours missed due to other reasons in the last seven days (Q3);
- hours actually worked in the last seven days (Q4);
- degree hepatitis C affected productivity while working (Q5);
- degree hepatitis C affected regular activities (Q6).

If any of the items Q1-Q6 will be presented as interval it will be replace by mean value for calculations.

WPAI outcomes are expressed as impairment percentages, with higher numbers indicating greater impairment and less productivity, i.e. worse outcomes.

The following four WPAI:SHP scores will be calculated and analyzed:

- absenteeism as percentage of work time missed due to hepatitis C:

$$100 \times \frac{Q_2}{Q_2+Q_4};$$

- presenteeism as percentage of impairment while working due to hepatitis C):

$$100 \times \frac{Q_5}{10};$$

- TWP (percentage of overall work impairment due to hepatitis C):

$$100 \times \frac{Q_2}{Q_2+Q_4} + \frac{Q_4}{Q_2+Q_4} \times \frac{Q_5}{10};$$

- TAI (percentage of general (non-work) activity impairment due to hepatitis C):

$$100 \times \frac{Q_6}{10}.$$

A score will be set to missing if one or more of the items Q1-Q6 that are needed for the calculation of the score is missing.

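### Read literally, the WPAI missing-item rule drops employed patients whom hepatitis C kept off work all week from the total work productivity impairment (TWP) score, although the plan's own formula gives them 100%

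*SAP*

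**What the plan says.** Work productivity belongs to a secondary objective (Protocol 8.2.2, SAP 3.1.2). Protocol 9.7.5 and SAP 10.2 derive four WPAI scores, one of which is TWP.

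- **Formula.** In Protocol 9.7.5, TWP is 100 times the sum "Q2/(Q2+Q4) + [Q4/(Q2+Q4)] * Q5/10". Q2 is hours missed because of hepatitis C, Q4 is hours worked, and Q5 is the 0 to 10 rating of impairment while working. SAP 10.2 uses the same three items.
- **Missing items.** SAP 10.2 states: "A score will be set to missing if one or more of the items Q1-Q6 that are needed for the calculation"; that is, one absent input is enough to lose the score. Protocol 9.7.5 has the same rule and adds: "No imputation will be performed for missing items".
- **Skip pattern.** In Protocol Annex 2, item 4 asks "During the past seven days, how many hours did you actually work", with the instruction "If '0', skip to question 6". Q5 is therefore blank by design for anyone who worked no hours.
- **Scoring reference.** SAP 10.2 says that the WPAI "will be evaluated according to the WPAI:SHP v2.0 scoring manual", and Protocol 9.7.5 also points to a WPAI-SHP manual. Neither document reproduces a special case from it, and neither has a rule for Q4=0.

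**The concern.** A designed skip is treated in the same way as an unanswered question. An employed patient who missed the whole week because of hepatitis C has no Q5, so a program that applies the formula and the rule as written returns TWP as missing. That patient's TWP is nevertheless fully determined by Q2 and Q4, and it is the highest value on the scale.

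Two outputs would suffer. The TWP summaries would omit the patients with the greatest work loss, and a patient fully absent at baseline would also leave the change from baseline (the TWP tables follow shell 3.6.1.1, which includes change). In addition, the same patient stays in the absenteeism table at 100%. The two tables would then rest on different patients, and mean TWP could be below mean absenteeism, although no single patient's TWP can be below that patient's absenteeism.

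**Working it through.** The plan states no figure for this point, so there is nothing to reproduce. The check applies the documents' own formulas, skip pattern and missing-item rule in turn.

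**Step 1: the score when Q4=0 and Q2>0.** Take Q1=yes, Q2=40, Q4=0.

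- Absenteeism = 100*40/(40+0) = 100%.
- TWP (protocol) = 100*{40/40 + [0/40]*Q5/10} = 100*{1 + 0} = 100%. The result is 100.0 at Q5 = 0, 3, 5 and 10.
- The SAP formula lacks the protocol's outer brackets, but it also gives 100.0 at each of these Q5 values, because the Q5 term is zero. The missing brackets are a separate matter, and the present problem remains once they are restored.
- TWP under the missing-item rule, read literally: missing, because Q5 is blank.

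**Step 2: who is affected among patients with Q5 skipped by design.**

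| Situation | TWP by the formula | TWP by the literal rule |
|---|---|---|
| Not employed (Q1=no) | not applicable | missing |
| Employed, Q2>0, Q4=0 | 100% | missing |
| Employed, Q2=0, Q4=0 (for example, a week of leave) | 0/0, undefined | missing |

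Only the second row has a computable score, and that score is always the maximum.

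**Step 3: effect on the mean.** Let f be the share fully absent because of hepatitis C, among employed patients with a computable TWP, and m the mean TWP of the others. The mean with everyone included is (1-f)*m + f*100. The literal rule reports m. The shortfall is f*(100-m).

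The documents give neither f nor m. The values below are assumptions, to show size only.

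| m | f=1% | f=2% | f=5% | f=10% |
|---|---|---|---|---|
| 10 | 0.9 | 1.8 | 4.5 | 9.0 |
| 20 | 0.8 | 1.6 | 4.0 | 8.0 |
| 30 | 0.7 | 1.4 | 3.5 | 7.0 |

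In counts, assume 60 employed patients at a visit and m=20. With 1, 3 or 6 fully absent, the full mean is (59*20+100)/60 = 21.3, (57*20+300)/60 = 24.0 or (54*20+600)/60 = 28.0. The literal rule reports 20 each time.

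**Step 4: coherence with absenteeism.** For every patient, TWP equals absenteeism plus a term that is not negative. Let a be the mean absenteeism of the others, so a is at most m. The absenteeism table reports (1-f)*a + f*100, and the TWP table reports m. The order of the means reverses when f*(100-a) exceeds m-a. In the simplest case the others lose time only through absence (Q5=0), so a=m. With a=m=20 and f=5%, mean absenteeism is 0.95*20+5 = 24.0 and reported mean TWP is 20.0.

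**The case against.** The best defence is textual. The rule does not say that any blank item voids a score; it covers items needed for the calculation. At Q4=0 the weight of Q5 is zero, so Q5 can be read as not needed. Both documents also defer to a scoring manual that may settle the case. This stands as a possible escape, and it is why the point is limited to a literal reading. It does not remove the need for a rule: neither document writes the exception, and a programmer who codes the stated formula and rule gets missing. SAP 10.2 does settle another WPAI edge case (answers given as an interval), so this one need not be left to interpretation.

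A reader might go further and infer that the rule removes only patients at the maximum score. The documents do not support that. The skip depends on Q4 alone, so it also catches employed patients with Q2=0 and Q4=0, whose TWP is undefined; the rule also removes patients who left a needed item blank for ordinary reasons.

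The limited stakes are also a fair point. WPAI is secondary and descriptive, with no model or test specified for it, unlike the ANCOVA for EQ-5D-5L and PAM-13. SVR12 and safety are untouched. The loss is partly visible, because absenteeism, Q2 and Q4 have their own tables with the number of valid measurements. That lets a careful reader notice the gap, but it does not correct the TWP mean.

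**Conclusion.** The point holds for the literal reading of the rule together with the skip pattern. Employed patients with Q2>0 and Q4=0 lose a TWP score that the plan's formula fixes at 100%. If any such patients exist, mean TWP at that visit is biased downward and can fall below mean absenteeism.

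The direction is certain; the size is not. It is f*(100-m), or 0.7 to 9.0 points over the assumed ranges f=1% to 10% and m=10 to 30, and zero if no patient was fully absent. The documents give no employment rate, no frequency of full-week absence and no expected TWP, so no specific figure should be attributed to this trial. A reader might also infer that the change from baseline is biased in a known direction. That would need full absence to be more frequent at some visits than at others, on which the documents are silent.

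The correction should be made: it concerns a stated rule acting on a secondary-objective score, and the remedy costs almost nothing.

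**What to change.** Add to SAP 10.2, and align Protocol 9.7.5:

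- If Q1=yes, Q2>0 and Q4=0: absenteeism = 100%, TWP = 100%, presenteeism not applicable. This evaluates the existing formula and is not imputation, so it does not conflict with the rule against imputing items.
- If Q1=yes, Q2=0 and Q4=0: absenteeism and TWP are undefined and set to missing. This needs its own line, because for absenteeism no item is missing and the present rule does not cover 0/0.
- Report the number of patients in each of these two situations at every visit, beside the WPAI scores.

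If the scoring manual already contains such a rule, the SAP should state it. The cost is a short addition to the text and about one line of code. No new data are needed.

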### **10.3 PSP**

The information about utilization and the contribution of the patient support program (PSP) to disease control, treatment continuation and patient satisfaction will be reported as descriptive statistics only in accordance with section 7.1.

All percentages will be calculated with number of patients, which have utilized any components from the AbbVie Patient Support Program as a denominator (valid percent).

The following parameters will be analyzed on all applicable visits:

- the number of patients who participated in the PSP;
- the number of patients who utilized any components from the AbbVie PSP since the last visit;
- level of general satisfaction of the AbbVie PSP;
- the AbbVie PSP’s relevance to patients’ needs;
- frequency of and satisfaction from using education and information materials.

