**Table 3.11.1 PSP results**

The core population

Page X of X

| Visit
Parameter   | ABBVIE REGIMEN + RBV          |  | ABBVIE REGIMEN - RBV          |     | Overall
(N = XX)
n (%) |
|--|-------------------------------|--|-------------------------------|-----|------------------------------|
|  | 12 weeks
(N = XX)
n (%) |  | 12 weeks
(N = XX)
n (%) |     |                              |
| Patient who gave consent to participate
in the AbbVie patient support program | XX (XX.X)                     |  | XX (XX.X)                     | ... | XX (XX.X)                    |
| Interim early on-treatment visit   |                               |  |                               |     |                              |
| Patients who utilized any components
from the AbbVie patient support program  | XX                            |  | XX                            | ... | XX                           |
| n  | XX (XX.X)                     |  | XX (XX.X)                     |     | XX (XX.X)                    |
| Yes  | XX (XX.X)                     |  | XX (XX.X)                     |     | XX (XX.X)                    |
| No   | XX (XX.X)                     |  | XX (XX.X)                     |     | XX (XX.X)                    |
| Level of satisfaction of the AbbVie PSP in general                               |                               |  |                               |     |                              |
| n  | XX                            |  | XX                            | ... | XX                           |
| Very good  | XX (XX.X)                     |  | XX (XX.X)                     |     | XX (XX.X)                    |
| Good   | XX (XX.X)                     |  | XX (XX.X)                     |     | XX (XX.X)                    |
| Satisfactory   | XX (XX.X)                     |  | XX (XX.X)                     |     | XX (XX.X)                    |
| Poor   | XX (XX.X)                     |  | XX (XX.X)                     |     | XX (XX.X)                    |
| Did the Program address you need?  |                               |  |                               |     |                              |
| n  | XX                            |  | XX                            | ... | XX                           |
| Yes, fully   | XX (XX.X)                     |  | XX (XX.X)                     |     | XX (XX.X)                    |

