| Patients who utilized any components
from the AbbVie patient support program |                               |  |                               |  |                              |
| n   | XX                            |  | XX                            |  | XX                           |
| Yes   | XX (XX.X)                     |  | XX (XX.X)                     |  | XX (XX.X)                    |
| No  | XX (XX.X)                     |  | XX (XX.X)                     |  | XX (XX.X)                    |
| Educational and information material  |                               |  |                               |  |                              |
| Frequency   |                               |  |                               |  |                              |
| n   | XX                            |  | XX                            |  | XX                           |
| Usually daily   | XX (XX.X)                     |  | XX (XX.X)                     |  | XX (XX.X)                    |
| Several times per week  | XX (XX.X)                     |  | XX (XX.X)                     |  | XX (XX.X)                    |
| ...   | ...                           |  | ...                           |  | ...                          |
| Printed   | XX (XX.X)                     |  | XX (XX.X)                     |  | XX (XX.X)                    |
| EoT   |                               |  |                               |  |                              |
| ...   | ...                           |  | ...                           |  | ...                          |
| Early post-treatment visit  |                               |  |                               |  |                              |
| ...   | ...                           |  | ...                           |  | ...                          |
| SVR12   |                               |  |                               |  |                              |
| ...   | ...                           |  | ...                           |  | ...                          |

N: the number of subjects in the core population.  
n: the number of valid measurements.

EoT: end of treatment.

SVR12: sustained virological response at 12 weeks after EoT.

Percentages are calculated from the number of subjects in the core population. For PSP questionnaire percentages are calculated from the number of subject in the core population who gave consent to participate in the AbbVie patient support program

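### SAP 10.3 divides every patient support program (PSP) percentage by program users, which does not work for utilisation or participation and contradicts the Table 3.11.1 footnote

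*SAP*

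**What the plan says.** SAP 10.3 limits the PSP analysis to descriptive statistics under section 7.1 and then sets one denominator: "All percentages will be calculated with number of patients, which have utilized any components from the AbbVie Patient Support Program as a denominator". It labels this rule valid percent. The parameters listed under it include "the number of patients who participated in the PSP" and "the number of patients who utilized any components from the AbbVie PSP since the last visit", followed by general satisfaction, relevance to needs, and frequency of and satisfaction with the educational materials.

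Table 3.11.1 has a row beginning "Patient who gave consent to participate", shown as n (%). At each visit it has a block beginning "Patients who utilized any components", with n, Yes and No lines, the last two again as n (%). Its footnote gives two denominators. The general one is: "Percentages are calculated from the number of subjects in the core population". The other is: "For PSP questionnaire percentages are calculated from the number of subject in the core population who gave consent to participate".

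Three other places bear on the point:

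- **SAP 7.1** sets a default denominator of subjects with non-missing data unless something else is specified.
- **SAP 16** drops the PSP regression because PSP usage is always Yes.
- **The PSP questionnaires annexed to the protocol** tell a patient who has used no component since the last visit to skip the remaining questions.

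**The concern.** A percentage of users among users carries no information about uptake, yet uptake is one of the things the section sets out to describe. The table footnote gives the programmer a different instruction for the same rows, and nothing in the SAP says which prevails. The footnote also fails for some rows: patients who skip the satisfaction items as instructed stay in the denominator.

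The PSP satisfaction and utilization questionnaires are listed secondary variables (Protocol 9.3.2, SAP 3.2.2). With the PSP regression dropped in SAP 16, these descriptive percentages are all that remains of the PSP analysis in Protocol 9.7.6. What is at stake is whether they mean what their row labels say.

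**Working it through.** The documents give no PSP figure, so there is none to reproduce. The check applies each text to each type of row.

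**Notation.** N = core population; C = core patients who consented to the PSP; U = users since the last visit at a given visit; S = users giving a particular answer to a satisfaction, needs or frequency item. Users are taken to be consenters, and every consenter is taken to return a questionnaire, so the No count is C − U.

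| Row of Table 3.11.1 | SAP 10.3 | Footnote |
|---|---|---|
| Consent / participation | C/U | C/N |
| Utilisation, Yes | U/U | U/C |
| Utilisation, No | (C − U)/U | (C − U)/C |
| Satisfaction, needs, frequency | S/U | S/C |

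**What follows without numbers.** Under SAP 10.3, Yes is 100% for any U > 0. No is not a proportion, and it exceeds 100% once non-users outnumber users. Participation is at least 100%. Under the footnote, the consent row is a proper proportion, and so is utilisation. The categories of a satisfaction item, however, sum to U/C rather than 100%, even if every user answers.

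**Single illustration (assumed counts).** C = 100, U = 70, and 63 users rate the program good or very good.

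- Utilisation: 70/70 = 100% under SAP 10.3; 70/100 = 70% under the footnote.
- Good or very good: 63/70 = 90% under SAP 10.3; 63/100 = 63% under the footnote.

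**Range (assumed counts).** N = 158 is the planned sample size, used here as the core population. C = 120 is assumed, and half of the users are assumed to answer very good. Each cell shows SAP 10.3, then the footnote.

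| U | Yes | No | Consent | Very good |
|---|---|---|---|---|
| 120 | 100.0% / 100.0% | 0.0% / 0.0% | 100.0% / 75.9% | 50.0% / 50.0% |
| 96 | 100.0% / 80.0% | 25.0% / 20.0% | 125.0% / 75.9% | 50.0% / 40.0% |
| 72 | 100.0% / 60.0% | 66.7% / 40.0% | 166.7% / 75.9% | 50.0% / 30.0% |
| 48 | 100.0% / 40.0% | 150.0% / 60.0% | 250.0% / 75.9% | 50.0% / 20.0% |

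For U = 72: No is 48/72 = 66.7% against 48/120 = 40.0%; consent is 120/72 = 166.7% against 120/158 = 75.9%; very good is 36/72 = 50.0% against 36/120 = 30.0%.

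The first line is the case in which every consenter is a user. Utilisation and satisfaction then agree, and only the consent row differs. All rows agree only when C = U = N.

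**Time frame.** SAP 10.3 does not say when use must have occurred. If it means users at any visit, the per-visit rate can fall below 100%: with an assumed 110 ever-users and 96 users at the visit, 96/110 = 87.3%. An ever-used rate would still be 100%, and the conflict with the footnote would remain.

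**Visit coverage.** Protocol Annex 4 gives the mid-treatment questionnaire only to patients on 24 weeks of therapy, while Table 3.11.1 has mid-treatment rows with an Overall column. Dividing those rows by all consenters would include any 12-week patients, who have no such visit.

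**The case against.** The strongest objection is SAP 16. It says PSP usage is always Yes, in a SAP version dated 02 Feb 2018, after the planned end of data collection in Aug 2017. If that means every consenter used the program at every visit, users and consenters are the same people, and utilisation and satisfaction come out alike under both texts. This stands as a limit on the size of the effect, which may be nil for those rows. It does not settle the matter. SAP 16 could refer to participation only, and both the questionnaires and the table shell provide a No answer.

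It can also be argued that SAP 10.3 lists participation and utilisation as numbers of patients, and that its valid-percent rule was aimed at the items only users answer, where it is the right choice. That is a plausible account of the intention. But the rule is written for all percentages, and the shell prints a percentage on the consent, Yes and No rows.

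Three stronger readings are tempting and are not supported:

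- **That the footnote counts non-users as dissatisfied.** It does not. No non-user enters Poor or any other category; the categories simply sum to less than 100%.
- **That the utilisation information is lost.** It is not. The shell prints counts for consent, Yes and No, and the number of valid measurements above each item, so a reader can recompute the proportions.
- **That the footnote is wrong throughout.** Its first sentence appears to give the consent row the core population, which is suitable, and consenters are close to the right denominator for utilisation.

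**Conclusion.** Wrong as written, and minor. Taken literally with users at the visit, the SAP 10.3 denominator makes the utilisation Yes row 100% by construction, turns the No row into a ratio to users, and puts participation at or above 100% if all users are consenters. It also contradicts the Table 3.11.1 footnote. The footnote is not a full repair, because it dilutes the items that non-users are told to skip.

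The size cannot be determined from the documents. It runs from no difference in utilisation and satisfaction, when every consenter is a user at every visit, to a gap that grows with the share of non-users. All counts used above, including the core population of 158, are assumptions and not study data. The results are descriptive; no test or model depends on them, and SVR12 is unaffected.

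**What to change.** State the denominator by row, in the same words, in SAP 10.3 and in the Table 3.11.1 footnote:

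- **Participation (consent):** the analysis population of the table.
- **Utilisation at a visit:** PSP participants with a questionnaire at that visit.
- **Satisfaction, needs and frequency items:** users at that visit who answered the item.

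Carry the same footnote to Tables 3.11.2 and 3.11.3, with the population changed accordingly. It would also help to say in SAP 16 whether usage means participation or utilisation at each visit. The cost is wording and the matching program denominators; no new data are needed.
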